### 3.3.3 POST-OPERATIVE VISITS (DAYS 1 – 60)

All subjects implanted with a study lens will be seen for 1 Day, 1 Week, 1 and 3 Month assessments as outlined in Appendix A.

IN ADDITION, the second eye will be implanted during this time period. It is recommended (at the final discretion of the Investigator), to complete this procedure as close to the 1 Week Visit (after first eye cataract extraction) as possible. Since second eye assessments will be completed on the same schedule as the first eye assessments (see Appendix A – Table 1), this will allow the subject further convenience in attending as many post-operative bilateral assessment visits as possible.

The Investigator will carry out the second eye surgical procedure as specified in the Surgical Procedure Manual and the following details will be captured in both Source Documents and eCRFs:

- Date of surgery
- Operative eye
- Cohort 1 or Cohort 2
- Incision location and size
- Ophthalmic Viscoelastic Device (OVD) used
- All medication used pre-, intra-, and post-operatively (ophthalmic and systemic)
- Model, serial number, and diopter of HMIOL implant components
- Toric IOL power and axis orientation (for toric IOL)
- IOL injection device

Once the subject is confirmed stable post-surgery, provide post-operative instructions and discharge.

NOTE: All concomitant medication, AE, and SAE collection must be continued throughout the course of the study. Any outcomes resulting in unacceptable RRE (as determined between Investigator and Subject), can be addressed with spectacles, a contact lens, or surgical correction. Any PO surgical adjustments to outcomes (corneal refractive surgery, lens exchange, etc.) will be carried out as determined to be in the best interest of the subject. The course of treatment will follow the Investigators SOC and be collected as a concomitant procedure.

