## 2.0 OBJECTIVES

The objective of this pilot study is to demonstrate the safety and efficacy of the HARMONI™ Modular Toric IOL in patients with pre-existing astigmatism.

The specific objectives are:

- To evaluate endothelial cell loss after an intraoperative optic exchange.

- To evaluate refractive outcomes, astigmatism correction with HMTIOL used in primary surgery.

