Keratometry	X					X	X
Axial Length	X						
Anterior Chamber Depth	X						
IOL/Toric Power Calculation	X						
Slit Lamp Examination	X			X	X	X	X
Specular Microscopy	X						X
IOP	X			X	X	X	X
Pupil Size	X	X	X				
Surgery / IOL implantation		X	X				
Intraoperative Exchange			X				
				X	X	X	X
IOL Rotational Stability		X	X	X	X	X	X
Dilated Fundus Exam	X						X

 All testing to be conducted on both eyes Will include pregnancy test if applicable If UCDVA is < 20/40, perform Pinhole (PH) vision Measurements via biometry will be utilized for both calculations and data capture To be reviewed and approved by the Sponsor Dilated slit lamp photo submitted to IOL Stability Reading Center

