5. Statistical Analyses*5.1. General Statistical Methods*

In general, analyses will be provided based on available data.

For continuous measures, descriptive summary statistics will include the number of observations, mean, standard deviation, median, minimum, maximum, as well as the number of eyes with results not reported. For continuous measures analyzed as changes from earlier visits, the 95% confidence interval for change will also be reported. Continuous measures may also be dichotomized or otherwise split into clinically meaningful categories and additionally analyzed as categorical measures.

For categorical measures, the percentage and number of cases for each condition (e.g., 20/40 or better) will be reported. The number of eyes without results will be omitted from the numerator and denominator of such calculations (i.e. no imputation will be performed).

Any calculated p-values will be based on nominal calculations with no adjustment for multiplicity. No imputation for missing data will be performed.

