5.9. Effectiveness Analyses

All endpoints listed above will be summarized by study visit and cohort as described in section 5.1 based on the Implanted Eye Population. BCDVA will also be summarized based on the Best-case population as suggested by ISO.

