7.1.2. IMPLANTED-EYE POPULATION

The Implanted-Eye Population consists of eyes with successful HMTIOL or HMIOL implantations during surgeries. Since it is important to evaluate HMTIOL or HMIOL's effect on the study eyes, the assessment of ECC, slit lamp examination, intraocular pressure (IOP), and dilated fundus examination (DFE) will be based on the implanted-eye population. It should be noted that the ECC comparison between Cohort 1 and Cohort 2 of this study will be based on the subjects with successful implants in both eyes and have available ECC data at 3 months.

Additionally, the UCDVA, BCDVA, prediction error, and meridian rotation will be evaluated based on the implanted-eye population.

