7.1.3. PER PROTOCOL POPULATION

The Per Protocol (PP) Population contains eyes with successful HMTIOL or HMIOL implantations during surgeries and do not have major protocol deviation (such as improperly enrolled in the study or lens power calculation errors) and will be considered the primary population for effectiveness outcomes. The effectiveness outcomes (UCDVA, BCDVA, and prediction error) will be evaluated based on the per protocol population.

The protocol deviations will be reviewed by ClarVista clinical personnel prior to analysis.

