**8. Interim Analyses**

There are no plans for formal interim analyses for the purposes of study modification or possible early termination. Any interim analyses will be administrative in nature and results will not be distributed to Investigators or subjects to prevent bias from exposure to accruing study results.

SAP CP-00002

[figure not shown]
ClarVista Medical, Inc.

9. Deviations from the Statistical Analysis Plan

Any deviations from the Statistical Analysis Plan will be noted and described with appropriate statistical and clinical rationale as needed. Discrepancies from the Investigational Plan are noted. The primary change is the use of a paired t-test instead of a two-sample t-test to test the primary hypothesis. This change more appropriately accounts for within-patient correlation in ECC. A secondary change was the use of "ECC" rather than "ECL" in Sections 6 and 7 above. ECL is defined in the protocol as follows: "a negative ECC percent change represents an ECC percent loss (ECL)." Since a comparison of 3-month to Pre-operative data may not always result in a measurable loss (e.g., due to measurement error of instrumentation combined with minimal actual ECC loss), ECC is determined to be a more appropriate term.

10. References

1. ISO 11979-7:2014 Ophthalmic implants — Intraocular lenses — Part 7: Clinical investigations.

Alcon - Business Use Only

Document: TDOC-0055985

Status: Effective

Effective Date: 24-Apr-2019

Version: 1.0; CURRENT; Most-Recent; Effective

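### Eyes surgically corrected for residual error before the 3-month visit are pooled as observed, so their corrected values can count as lens performance, and the SAP's SSI rate may not show the correction

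*Protocol*

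**What the plan says.** **Permission for surgery.** Protocol 3.3.3 lets residual refractive error that investigator and subject find unacceptable be handled with glasses, a contact lens or surgery. On surgery it says that "Any PO surgical adjustments to outcomes (corneal refractive surgery, lens exchange, etc.) will be carried out as determined" to serve the subject's interest. This follows the site's standard of care and is entered as a concomitant procedure. No date limit is given. The 3-month visit falls at Day 80-100 (Protocol 3.3.4).

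**Analysis rules.** SAP 5.1: "In general, analyses will be provided based on available data", with no imputation. SAP 5.9: "All endpoints listed above will be summarized by study visit and cohort as described in section 5.1 based on the Implanted Eye Population". Membership of that population is settled by successful implantation at surgery (SAP 7.1.2). The Per Protocol set keeps eyes that "do not have major protocol deviation (such as improperly enrolled in the study or lens power calculation errors" (SAP 7.1.3). Misalignment compares the final lens meridian with the plan (SAP 5.9.4). Rotation runs from Day 0 to each visit (SAP 5.9.5).

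**SSIs.** The protocol's synopsis and section 7.1 list SSIs as a safety endpoint without requiring a link to the device. SAP 5.4 and 5.5 count device-related SSIs only, and SAP 2 states that its analyses replace those of the Investigational Plan.

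**Incomplete text.** Protocol 8.3 stops mid-sentence where it mentions a possible further split of the eye data. Several analysis sections carry redactions, among them Protocol 8.3.1.2, 8.3.2.1, 8.3.2.4 and 8.3.2.5 and SAP 5.9.1 and 5.9.3.

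**The concern.** A 3-month refractive table is normally read as what the implanted lens achieved. If an eye missed its target and was then treated on the cornea, or had its optic turned or exchanged, its 3-month value shows the lens plus the rescue. Under the visible rules that value is averaged with those of untouched eyes and nothing marks it. The mixing is between eyes: some never re-operated, some measured after a second procedure.

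This is foreseeable for a lens built so that its optic can be exchanged or adjusted after implantation (Protocol 5.1). The SSI rate is where a reader would look for such eyes, and the SAP version of it is the narrower one. A power-prediction miss corrected on the cornea and judged unrelated to the device could be absent from the SSI rate while its improved result stays in the effectiveness tables.

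**Working it through.** **1. Does any visible rule remove or separate these eyes?**
- Implanted-Eye Population (SAP 7.1.2): fixed at surgery, with no later exit.
- Per Protocol set (SAP 7.1.3): removes major deviations. Surgery that the protocol allows is not naturally a deviation; this is an inference, since the SAP does not say so. An eye re-operated after a lens power calculation error would drop out, but because of the error.
- Discontinuation (Protocol 4.5): lists explantation in both eyes. Corneal surgery, optic repositioning and optic exchange are not listed.
- Best Case set (Protocol 8.2.4): its refractive-surgery criterion reads as preoperative, and the set serves BCDVA only.

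None does so for corneal surgery, repositioning or optic exchange.

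**2. Do the by-visit tables rescue the result?** Partly. Manifest refraction is taken at 1 month (Day 30-60) and 3 months (Day 80-100) after surgery (Protocol Appendix A, Table 1). A correction between those visits leaves an untreated 1-month value. One before the 1-month refraction leaves none. UCDVA and lens position are recorded from Day 1. No table identifies the corrected eyes.

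**3. Direction by endpoint.**
- Manifest cylinder, cylinder reduction, absolute prediction error, and usually UCDVA: a successful correction favours the lens.
- Misalignment: a realigned lens counts as well placed, because only the final meridian is used.
- Rotation: not fixed. A lens that turned 15° and was put back scores about 0°. A lens placed 15° off plan and then realigned scores about 15° and fails the <10° category.
- Signed MRSE prediction error (the SAP 5.9.3 formula is signed): not fixed. Correcting a myopic or a hyperopic miss moves the mean in opposite directions.

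**4. Denominators.** The SAP plans 25 evaluable subjects and about 20% dropout: 25 / 0.80 = 31.25, rounded up to 32. This reproduces its figure.

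**5. Effect of one affected eye.**
- Percentage, if the eye changes category: 1/32 = 3.1 points; 1/25 = 4.0 points. If only 16 Cohort 2 eyes were toric (assumed), 1/16 = 6.3 points for the cylinder endpoints.
- Mean cylinder with 32 eyes, for an assumed correction of 0.5, 1.0 or 1.5 D: 0.5/32 = 0.016 D, 1.0/32 = 0.031 D, 1.5/32 = 0.047 D.
- Mean signed MRSE error: 1.0/32 = 0.031 D per 1 D corrected, in either direction.

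**6. How many eyes?** The documents give no rate for this lens. As illustration only, Protocol 1.0 cites 6.7% of eyes repositioned with another toric lens, and secondary procedures as high as 16% in some practices. Neither has a time frame, and one statement of the 16% is per patient.
- 0.067 × 32 = 2.1 eyes; chance of at least one = 1 − 0.933^32 = 0.89.
- At half that rate: 1.1 eyes; chance 0.66.
- At an assumed 2%: 0.6 eyes; chance 0.48.
- 0.16 × 32 = 5.1 eyes; 5/32 = 15.6 points.

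**7. ECC, for scale.** Postoperative specular microscopy is scheduled only at 3 months, so an intraocular re-operation before then would be included. An assumed extra loss of 5 to 20 points in one eye shifts the mean of 25 paired differences by 5/25 = 0.2 to 20/25 = 0.8 points. The standard error is 12.6 × √(2(1 − r)/25), which is 3.56 at r = 0 and 2.52 at r = 0.5 (r assumed). The shift is thus 0.2/3.56 = 6% to 0.8/2.52 = 32% of one standard error.

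**The case against.** The best reply is that the point rests partly on an absence, in documents whose analysis text is incomplete. A separation rule could sit in the sentence that breaks off in Protocol 8.3 or in a redacted block. That stands, and it limits the point to the visible text. The pooling rule and the narrowed SSI definition, however, are both stated in plain view.

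A second reply is that as-observed reporting is legitimate in a feasibility study. Protocol 8.3.2 calls effectiveness outcomes other than BCDVA exploratory, every procedure is recorded with its indication (Protocol 4.8.2), and 1-month results are reported. That too stands. It argues for keeping the as-observed tables, not against marking the affected eyes. SAP 5.5 also reports ISO Annex B adverse events, but neither document reproduces that list, so whether it would catch these corrections cannot be judged here.

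Three stronger readings are tempting, and the documents do not support them.
- **That the ECC comparison is compromised.** The paired set is described ("the ECC comparison between Cohort 1 and Cohort 2 of this study will be based on the subjects with successful implants in both eyes") and the change of test is noted ("The primary change is the use of a paired t-test instead of a two-sample t-test to test the primary hypothesis"). But the protocol's ECC methods are redacted and SAP 5.6 is one sentence, so the analysis text is plainly incomplete, and one eye shifts the mean by well under one standard error.
- **That the objective rules out later surgery.** Protocol 2.0 says "To evaluate refractive outcomes, astigmatism correction with HMTIOL used in primary surgery". Protocol 8.0 sets primary cataract surgery against intraoperative exchange, so the phrase more naturally separates the cohorts.
- **That a one-eye explant certainly stays in the tables.** Protocol 4.5 goes on to ask for one BCDVA visit after an explant before discontinuation, without saying both eyes. Follow-up may end there.

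**Conclusion.** The point holds for the visible text. Surgically corrected eyes can enter the 3-month manifest cylinder, cylinder-reduction, absolute prediction-error, UCDVA and misalignment tables as lens performance, and the SAP's SSI rate may not reveal them. The size is zero if no such surgery takes place, and otherwise up to 3.1 points (32 eyes) or 4.0 points (25 eyes) per affected eye. The means move by hundredths of a dioptre per eye under the assumed corrections. The number of affected eyes is unknown, and the cited background rates do not predict it.

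A reader might infer that every 3-month effectiveness figure is biased in favour of the lens; for rotation and signed MRSE error that does not follow. This is a modest reporting improvement, not a fault that undermines the study.

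**What to change.** 1. **SAP 5.4 and 5.5.** Report all SSIs by cohort, leaving out the planned Cohort 2 intraoperative exchange, with device-related SSIs as a subset.
2. **SAP 5.9.** Flag any eye with a postoperative surgical refractive procedure, optic repositioning or exchange, or explant before the 3-month visit. Keep the as-observed tables. Add a supplementary 3-month display in which each flagged eye takes its last observed pre-procedure value, with the visit named. Label it a sensitivity display outside the no-imputation rule of SAP 5.1. Count and list individually any flagged eye with no such value: dropping it silently could remove the worst early failures. Rotation and misalignment change in this display only if the lens itself was moved, exchanged or removed.
3. **SAP 5.6, optional and minor.** If the redacted ECC text does not already do so, show the ECC comparison with and without subjects who had an intraocular re-operation.

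No new visit or assessment is needed, because the procedures are already recorded. The cost is a few lines of SAP text, one extra table set, and possibly slightly less favourable figures in the supplementary display.

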### 3.3.4 3 MONTH VISIT (DAY 80-100)

Bilateral assessments will be completed as indicated in Appendix A – Tables 1 and 2. In the event the second eye is out of window at this visit, the subject will return in-window to complete second eye assessments.

### 3.3.5 UNSCHEDULED VISITS

If at any time during the study, outside of the above scheduled visits, the subject requests or the Investigator determines the subject should be assessed, an unscheduled visit may occur. Adverse events and concomitant medications will be recorded and assessments deemed necessary by the Investigator should be performed on either or both eyes.

If a subject is seen for multiple visits during a given visit window, the data from a visit that is intended to meet the protocol requirements for the scheduled visit should be captured in the visit eCRF. Where such a determination cannot be made, the first visit within the scheduled visit window will be used for completion of the protocol required visit. If assessments are missing from that visit, however captured at subsequent visits within window, those assessments can be collected as part of the protocol visit. In such a circumstance, the visit date will remain consistent with the first visit established within the visit window, per the scenario above. Any additional and applicable data captured and associated with the Study Eye will be captured as an Unscheduled Visit.

### 3.3.6 MISSED VISITS

If a subject misses any scheduled visit and cannot be seen prior to the start of the next visit window, the visit will be considered "missed."

## 4.0 STUDY METHODS

Prior to recruitment of any subjects into the study, review and written approval of the protocol and informed consent must be obtained from the Institutional Review Board (IRB) or Ethics Committee (EC) by each participating clinical site.

### 4.1 INFORMED CONSENT

Informed consent must be obtained and documented in writing prior to the initiation of any study procedures. The subject (or the subject's legally authorized representative) must be allowed sufficient time to thoroughly read (or have explained), the informed consent form. The Investigator or his/her designee should answer any questions that the subject/representative might have. If the subject agrees to participate in the study, (i.e. provides informed consent) the subject/representative must sign two copies of the informed consent form. The witness and the Investigator must also sign both copies of the informed consent form. One copy of the informed consent form should be given to the subject/representative. If applicable, it will be provided in a certified translation of the local language. As part of the consenting process, the subjects will be informed of their right to treatment for any injuries related to the study. Any and all such treatment if necessary, will be paid for by the Sponsor to the extent it is not covered by a subject's healthcare coverage (subject to local ethics committee approval). Completion of the consenting process as well as the date of the subject's signature on the informed consent form should be noted in the subject's medical chart.

Subjects who complete the informed consent process will be screened for eligibility. Screened subjects will be recorded on site-specific screening logs and once they are determined as being eligible, they will be enrolled into the study and an HMIOL order placed with the Sponsor if necessary. All eligible subjects will receive a stipend to attend scheduled study visits as an allowance for food, time, and travel expenses.

### 4.2 ASSIGNMENT OF SUBJECT IDENTIFICATION

A unique and sequential subject identification number (ID) will be assigned at screening and never duplicated for another subject. This ID will be used on all study-related documents. To maintain confidentiality, the subject's name will not be recorded on any study document other than the informed consent form.

### 4.3 SCREEN FAILURE

A record of screen failures and the reasons for the screen failures will be recorded in the subject source documents and captured in the eCRF for summary.

#### **4.4 SUBJECT COMPLETION**

The subject has completed the entire study when the HMTIOL/HMIOL has been implanted and / or the Optic Exchange completed and the Sponsor receives completed electronic Case Report Form (eCRF) documentation for all visits and a Study Exit eCRF. Subjects who require further follow-up for an AE will be followed according to Section 6.3.4.

A Study Exit eCRF must be completed for all subjects who complete the clinical investigation.

#### **4.5 SUBJECT DISCONTINUATION**

A subject **MUST** be discontinued prior to the final study visit for any of the following reasons:

- Death
- Subject is enrolled and scheduled for surgery but is not implanted with an HMTIOL or HMIOL in at least one eye
- Surgical complication(s) unrelated to the investigational device preventing the implantation of the HMTIOL or HMIOL in both eyes (i.e. capsulorhexis tear, zonular rupture, evident zonular weakness or dehiscence, posterior capsular rupture, vitreous loss, posterior capsular plaque, significant detached Descemet's membrane, significant anterior chamber bleeding, iris incarceration or damage, corneal endothelial touch, unsuccessful/incomplete phacoemulsification, haptic and/or optic damage/haptic amputation)
- Explantation of the HMTIOL or HMIOL System in both eyes

If the study lens is explanted, one postoperative visit should be completed to record best-corrected distance visual acuity (BCDVA) before the subject is discontinued.

Subjects who withdraw from the study will be asked to complete procedures outlined in the 3 Month Visit (if withdrawn prior to that visit). Subjects who are terminated due to an AE will be followed, if possible, at least until resolution or stabilization of the AE. Subject withdrawals will be documented clearly on the source document and applicable eCRF.

Prior to discontinuing a subject, every effort should be made to contact the subject, schedule a final study visit, and obtain as much follow-up data as possible. Adverse events will be followed as described in Section 6.3.4. Discontinued subjects should be followed outside of the study protocol according to the Investigator's normal postoperative standard of care.

A Study Exit eCRF must be completed for all subjects who discontinue from the clinical investigation.

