#### 6.1.2 ADVERSE DEVICE EFFECT (ADE)

An ADE is any untoward or unintended effect, event, or response surrounding and with a causal relationship with the use of a medical device. This definition may include any event resulting from insufficiencies or inadequacies in the instructions for use or the deployment of the device or other device malfunctions. This definition includes any event that is a result of a user error and any event that affects a user of the device (i.e. caregiver, bystander, etc.).

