### 6.2 AE EVALUATION

AEs experienced in this study may be associated with the study device (i.e. ADE) or the study protocol as demonstrated in the following non-exhaustive list of examples:

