#### Study Device (ADE)

- IOL dislocation
- Explant due to haptic break/damage
- Explant due to base and/or optic damage

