**Study Protocol**

- Allergic reaction to dilating drops
- Lens remnants following surgery
- Capsular tear during surgery to implant study device

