5.5. Safety analyses

Adverse events and device deficiencies will be summarized at each study visit based on the safety population for Cohort 1 and Cohort 2 separately. The number and percentage of eyes reported with the ISO specified 3-month cumulative and persistent adverse events will be calculated for Cohort 1 and Cohort 2 separately.

Events will be summarized overall for the HMTIOL Cohort 2 and HMIOL Cohort 2. The corresponding one-sided lower 95% confidence limit will be calculated based on the binomial distribution and compared to the ISO SPE rate.

The number and percentage of eyes reported with HMTIOL-related adverse events during the study will be summarized for HMTIOL Cohort 1, HMTIOL Cohort 2, and HMTIOL-eye Cohort. The two-sided 90% confidence interval of the percentage will also be provided.

The number and percentage of eyes reaching BCDVA 20/40 or better, and worse than 20/40 at each visit will be prepared.

[figure not shown]
Rates for adverse events specified in ISO 11979-7:2014 Annex B for posterior chamber IOLs will be summarized at each visit.

Rates of device-related SSIs and device deficiencies will be summarized as described in 5.1 above.

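### Protocol 4.5 labels study-lens damage as unrelated to the device, and 6.2 gives a capsular tear at lens implantation as a protocol event; the device-attributed safety rates could be understated

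*Protocol*

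**What the plan says.** Protocol 4.5 lists reasons for which a subject must be discontinued. One is "Surgical complication(s) unrelated to the investigational device preventing the implantation of the HMTIOL or HMIOL in both eyes". A parenthesis introduced by i.e. then names the complications. They include capsulorhexis tear, posterior capsular rupture, contact with the corneal endothelium and, as the last item, "haptic and/or optic damage/haptic amputation".

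Protocol 6.2 says that adverse events "may be associated with the study device (i.e. ADE) or the study protocol as demonstrated in the following non-exhaustive list of examples". The device (ADE) examples include "Explant due to haptic break/damage" and "Explant due to base and/or optic damage". The study-protocol examples include "Capsular tear during surgery to implant study device".

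Protocol 6.1.2 requires a causal relationship with use of the device and then reads broadly: "This definition may include any event resulting from insufficiencies or inadequacies in the instructions for use or the deployment of the device". It also takes in any event that results from user error. Protocol 6.1.4 counts damage to the device or any part of it as a device deficiency, whatever the source and whether or not anyone is injured.

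SAP 5.5 uses the attribution: "The number and percentage of eyes reported with HMTIOL-related adverse events during the study will be summarized", by cohort and for all HMTIOL eyes, with a two-sided 90% confidence interval. SAP 5.4 restricts the secondary surgical intervention (SSI) endpoint to device-related interventions. Protocol 6.3.1 requires events judged related to the device to reach the sponsor within 24 hours.

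**The concern.** The haptics and optic are parts of the study lens, so a list that calls damage to them unrelated to the device is hard to square with the two sections that treat such damage as a device matter. The capsular tear example has a milder form of the same problem. A tear made while the lens is being deployed can meet the ADE definition, yet the only worked example of a tear sits on the protocol side.

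The stated rationale in Protocol 1.0 is that the optic can be exchanged or adjusted while sparing the capsule and endothelium. Capsular tears, endothelial contact and lens damage are among the events that bear on that rationale. If the wording leads a site to record a device-caused event as not device-related, the event leaves the summaries restricted to device-related events. The error would favour the device.

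**Working it through.** **Step 1. Lens damage, sections side by side.**

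| Section | Event | Treatment |
|---|---|---|
| Protocol 4.5 | Haptic or optic damage that prevents implantation | Labelled unrelated to the device |
| Protocol 6.2, device examples | Explant for haptic, base or optic damage | ADE |
| Protocol 6.1.4 | Any damage to the device, any source | Device deficiency |

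The events in 4.5 and 6.2 are not identical, because one precedes implantation and the other leads to removal. Section 6.1.4 covers both. One could read the word unrelated as a filter that admits only damage with an outside cause, such as surgeon handling. That does not rescue the label, because 6.1.2 and 6.1.4 both include user error. The inconsistency stands.

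**Step 2. Capsular tear.** Sections 4.5 and 6.2 agree with each other in placing tears outside the device. The tension is with 6.1.2, which can include an event resulting from deployment of the device. The 6.2 lists are tentative and illustrative, and surgery to implant the lens includes stages before any lens contact. This is an ambiguity, not a contradiction.

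**Step 3. Which results depend on attribution.**

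- Dependent: the HMTIOL-related adverse event rate and its interval (SAP 5.5); the device-related SSI rate (SAP 5.4), where a later intervention inherits the attribution of the event that led to it; and 24-hour ADE reporting (Protocol 6.3.1).
- Not dependent: all-cause adverse event summaries and ISO rates (Protocol 8.3.1.1, SAP 5.5), device-deficiency counts, and endothelial cell counts.

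**Step 4. Scale.** The plan states no expected device-related rate, so there is no figure of its own to reproduce. Inputs: up to 32 subjects with one eye in each cohort (Protocol 3.1), and a two-sided 90% interval (SAP 5.5). Assumptions: event counts of 0, 1 and 2, and exact Clopper-Pearson limits, since the SAP does not name the method for this interval.

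One eye moves a full cohort rate by 1/32 = 3.1 points. For x events in n eyes, the lower limit is the 5% quantile of Beta(x, n − x + 1) and the upper limit is the 95% quantile of Beta(x + 1, n − x). For x = 0 the lower limit is 0, and for n = 32 the upper limit is 1 − 0.05^(1/32) = 8.9%.

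| Events | n = 32: rate (90% CI) | n = 64: rate (90% CI) |
|---|---|---|
| 0 | 0% (0 to 8.9) | 0% (0 to 4.6) |
| 1 | 3.1% (0.2 to 14.0) | 1.6% (0.1 to 7.2) |
| 2 | 6.3% (1.1 to 18.4) | 3.1% (0.6 to 9.5) |

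The 64-eye column applies to the pooled HMTIOL rate only if every eye receives the toric lens. Cohort 2 may receive either lens, so its HMTIOL subgroup may be smaller than 32, and one eye would then move that rate by more than 3.1 points.

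**The case against.** A reader might infer that the device-related rates are understated, or that two tears would be reported as 0% where 6.3% occurred. The documents do not support that. Section 4.5 is a discontinuation rule that applies when implantation is prevented in both eyes, and it gives no instruction on coding adverse events. The investigator judges causality event by event under 6.2.1.4, and the not-related category is reserved for clear-cut cases. Section 6.4 adds a weekly review of causality. The two tears are assumed, as is their being device-caused and miscoded.

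A reader might also infer that the lists send optic-exchange events to the protocol side. Neither list mentions exchange: 4.5 concerns failure to implant, and the 6.2 example concerns surgery to implant.

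Capture elsewhere is good. Lens damage is reportable within 24 hours as a device deficiency, serious events are reportable within 24 hours whatever their cause, and 6.1.1 singles out capsular injury for timely reporting.

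All of this stands and limits the point to the attribution-dependent results. It does not remove it. Investigators make the causality judgement with these lists in front of them, and the related category in 6.2.1.4 covers device or protocol without separating them, so it does not by itself correct a steer from one to the other.

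**Conclusion.** The lens-damage label in Protocol 4.5 is inconsistent with 6.1.4 and 6.2 and must be reconciled. The capsular tear example in 6.2 is ambiguous against 6.1.2 and should be clarified. Together they could lead to understatement of the HMTIOL-related adverse event rate, the device-related SSI rate and 24-hour ADE reports. For reporting, the exposure is mainly to non-serious events without lens damage, since the others reach the sponsor by another route.

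The size is unknown. The 3.1 points per eye is a scale that assumes a full 32-eye cohort; it is not an estimate of bias. The conclusion rests on the wording alone and assumes that sites use the lists as guidance when assigning causality.

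**What to change.** 1. Reconcile Protocol 4.5 with 6.1.4 and 6.2 so that damage to the study lens is not labelled unrelated to the device. This concerns the label only and should leave unchanged who is discontinued.
2. Reword the capsular tear example in 6.2 so that a tear is a protocol event only when it is not caused by the device or its deployment.
3. State that capsular, zonular, endothelial and lens-damage events at or after first device contact, including during optic exchange, are each assessed for device relationship under 6.1.2. Those judged device-related are counted in the SAP 5.5 HMTIOL-related rate.

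The third item asks for an assessment and does not count events automatically. Treating every event after device contact as an ADE would replace causality with timing and could overstate the rate.

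The cost is a few text edits in the protocol and one sentence in the SAP, with no new visits or measurements. The device-related rate may look slightly less favourable.
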